7.1. Primary Safety Endpoint

- LV MSP feature-related complication-free rate between the 6 Month Visit and the 12 Month Visit in non-responders with the LV MSP on for any duration.

7.2. Primary Effectiveness Endpoint

- Proportion of the LV MSP Group subjects with Improved CCS from the 6 Month Visit through the 12 Month Visit.

8. Study Design

The SMART MSP study is designed as a prospective, single arm, multi-center, post-approval study to be conducted within the US.

8.1. Scale and Duration

The SMART MSP study’s sample size is approximately 586 subjects. See **Section 8.2** and **Section 12.3** for further details on the sample size and attrition estimate. This study will be conducted in approximately 60 US sites. All study required visits will be completed as part of

the subject's regularly scheduled clinic follow-up visits. The subject participation is complete when the final actively enrolled subject in the Non-Responder Group completes the 12 Month Visit. Study completion is anticipated to be approximately 36 months after first enrollment.

8.2. Treatment Assignment

All enrolled subjects will be programmed to conventional CRT from the point of enrollment visit to the 6 Month Visit. At the 6 Month Visit, the clinical composite score (CCS) will be calculated for each subject to determine the subject's responder status to conventional CRT. Subjects who are responders will be in the Responder Group and complete the study at the 6 Month Visit, as shown in **Figure 8.2-1**.

[figure not shown]
Subjects who are non-responders to conventional CRT based on the CCS calculation belong to the Non-Responder Group. The LV MSP feature will be enabled for these subjects from the 6 Month Visit through the 12 Month Visit. Those subjects who are able to receive the LV MSP therapy and achieve at least 93% of LV pacing are classified in the LV MSP Group, which is defined as meeting all of the following criteria:

- Subjects who have achieved at least 2 viable LV pacing vectors
- Subjects who have the LV MSP feature enabled
- Subjects who have achieved at least 93% of the LV MSP pacing

To determine whether an LV pacing vector is considered viable, the following criteria are recommended:

- The pacing impedance is not out-of-range per physician's programmed value
- No presence of PNS - the pacing capture threshold (PCT) plus 3V of safety margin should be less than PNS threshold
- LV PCT at $\leq 4.5V$ or demonstrated capture at $\leq 4.5V$

Figure 8.2-1: Study Design Flowchart

8.3. Justification for the Study Design

This study is designed to evaluate the therapy benefit provided by multisite pacing to those patients who are non-responders to CRT with single site LV pacing based on a clinical evaluation using the CCS. The study's primary endpoint of the Clinical Composite Endpoint (CCS) measures multiple components related to the improvement of patient's clinical status, including Patient Global Assessment, NYHA class change, heart failure event, and mortality rate. See **Section 11.5.1** for the definition and calculation used in the study. These measures are well-understood and widely accepted by the medical community.

9. Subject Selection

9.1. Study Population and Eligibility

Subjects included in the SMART MSP Study should be selected from the investigator's general patient population who received BSC Resonate family of CRT-D devices, and were indicated for CRT-D implantation per BSC labeled indication provided in **Section 9.1.1**. Investigators are responsible for screening all potential subjects and selecting those who meet the eligibility criteria for the study as described in **Sections 9.2** and **Section 9.3** below.

9.1.1. BSC Labeled Indication for CRT-D Implantation

The BSC's CRT-Ds are indicated for patients with heart failure who receive stable optimal pharmacologic therapy (OPT) for heart failure and who meet any one of the following classifications:

- Moderate to severe heart failure (NYHA Class III-IV) with EF \leq 35% and QRS duration \geq 120 ms
- Left bundle branch block (LBBB) with QRS duration \geq 130 ms, EF \leq 30%, and mild (NYHA Class II) ischemic or non-ischemic heart failure or asymptomatic (NYHA Class I) ischemic heart failure

9.2. Inclusion Criteria

Subjects who meet all of the following criteria (see **Table 9.2-1**) may be given consideration for inclusion in this clinical investigation, provided no exclusion criterion (see **Section 9.3**) is met.

Table 9.2-1: Inclusion Criteria

Inclusion Criteria	
1. Subjects who received de novo implantation of BSC's Resonate family of CRT-D devices with the LV MSP feature⁴ and BSC's ACUITY™ X4 LV Quadripolar leads. A Resonate family of CRT-D device upgrade from previous single or dual chamber pacemaker or ICD implantation is allowed.2. Subjects must meet BSC labeled indication for CRT-D implantation.3. Subjects must have a functional RA lead and RV lead implanted4. Subjects who are willing and capable of providing informed consent5. Subjects who are willing and capable of participating in all testing/visits associated with this clinical study at an approved clinical study center and at the intervals defined by this protocol6. Subjects who are age 18 and above, or of legal age to give informed consent specific to state and national law
---------------------------	---

9.3. Exclusion Criteria

Subjects who meet any one of the following criteria in **Table 9.3-1** will be excluded from this clinical study.

⁴ Resonate refers to all trademarked devices in this family of pulse generators, including RESONATE HF, RESONATE, VIGILANT, and MOMENTUM.

Table 9.3-1: Exclusion Criteria

Exclusion Criteria	
1. Subjects who received LV pacing prior to receiving the Resonate family of CRT-D system implantation.2. Subjects who received the LV MSP therapy post CRT-D implantation but prior to enrollment3. Subjects with documented history of permanent AF4. Subjects with documented permanent complete AV block5. Subjects who are expected to receive a heart transplant during the 12 months course of the study6. Subjects with documented life expectancy of less than 12 months7. Women of childbearing potential who are pregnant or plan to become pregnant over the course of the clinical trial. Note: For patients with uncertain pregnancy status, pregnancy tests should have been performed per site's standard clinical practice prior to CRT-D device implant.8. Subjects who enrolled in any other concurrent study or registry, with the exception of mandatory national or governmental registry, without prior written approval from BSC
---------------------------	--

10. Subject Accountability

10.1. Point of Enrollment

Subjects who meet all study eligibility criteria will be considered enrolled in the SMART MSP Study at the time of signing the informed consent form. All enrolled subjects meeting the eligibility criteria will be counted against the enrollment ceiling for the study. Any adverse event (AE) experienced post-enrollment by an actively enrolled subject that meets the protocol requirement for reporting must be recorded in the electronic case report form (eCRF) or alternative methods, if necessary. See **Section 20** for information on protocol requirements of AE reporting.

10.2. Point of Study Exit

All subjects enrolled in the clinical study shall be accounted for. An End of Study form is required for all study subjects and is completed following occurrence of any of these events:

- Subject completion of study participation
 - For subjects classified in the Responder Group, this is upon the completion of the 6 Month Visit.
 - For subjects classified in the Non-Responder Group, this is upon the completion of the 12 Month Visit.

- Subject withdrawal
- Subject death

10.3. Study Withdrawal

If a subject withdraws from the clinical study, the reason(s) shall be reported. If such withdrawal is due to problems related to the device safety or performance, the investigator shall ask for the subject's permission to follow the subject outside of the study.

Reasons for withdrawal may include but are not limited to:

- physician discretion
- subject choice to withdraw consent
- CRT-D device or LV lead explant
- lost to follow-up
- uncorrected LV lead dislodgment or undiscovered LV lead dislodgment until the 6 Month Visit
- LV lead revision prior to the 6 Month Visit

While study withdrawal is discouraged, subjects may withdraw from the study at any time, with or without reason, and without prejudice to further treatment. All applicable eCRFs up to the point of subject withdrawal and an "End of Study" eCRF must be completed. For subjects who are "lost-to-follow-up", the investigator/center staff must have at least three documented attempts to contact the subject prior to completion of the "End of Study" eCRF. Additional data can no longer be collected after the point at which a subject has been withdrawn from the study or withdraws his/her consent, regardless of the reason. All data queries should be resolved and all open adverse events should be closed or documented as chronic. Data collected up to the point of subject withdrawal may be used.

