11.5.14. LV MSP Settings Programming

Complete the programming of the LV MSP settings for subjects in the Non-Responder Group who have the LV MSP on. It is required that the LV MSP feature be turned on from the 6 Month Visit to the 12 Month Visit. The investigator may consider turning off the LV MSP feature if a subject experiences worsening symptoms. The subject may continue to receive conventional CRT. A rationale and study deviation are required if the LV MSP feature is turned off.

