12.1.1.3. Statistical Methods

Data from subjects who are deemed as a non-responder at the 6 Month Visit with LV MSP turned on for any duration of time from 6 Month Visit onward will be eligible for inclusion in the endpoint analysis. The LV MSP feature-related CFR between the 6 Month Visit and the 12 Month Visit will be calculated using Kaplan-Meier methodology. The evaluation period for each subject will begin at the time LV MSP was turned on (at or after the 6 Month Visit) and will continue through 180 days post-LV MSP being turned on.

⁶ BSC’s Enable MRI Clinical Study (IDE # G150181); performance goal for MR Scan related complication-free rate.

The 95% one-sided lower pointwise confidence limit of the LV MSP feature-related complication-free rate will be calculated via log-log methodology and compared to the performance goal of 90%. If the lower confidence limit exceeds 90%, the null hypothesis will be rejected.

Each subject's exact follow-up time in the period between the 6 Month Visit when the LV MSP is turned on through 180 days after the LV MSP is turned on will be included in the analysis due to the rate being calculated via Kaplan-Meier methodology. The subjects that reach the 6 Month Visit and have the LV MSP turned on but fail to reach 180 days of follow-up after the LV MSP was turned on (without experiencing an endpoint event prior to their end of follow-up in the period) will be censored at the time of their end of follow-up in the period. Because non-informative censoring cannot be assumed for these subjects, a tipping point analysis will be performed to determine the potential effects these censored subjects could have on the results if full information on each subject was present. The tipping point analysis will assign each subject that was censored between the 6 and 12 Month Visit as either having or not having an LV MSP feature-related complication. The tipping point will be determined by the point at which the endpoint results turn from passing (null hypothesis) to failing (null hypothesis rejected). An exact binomial test will be performed for the tipping point analysis.

In addition, a sensitivity analysis on the impact of "Unknown" related to the LV MSP feature will be performed. Subjects with a complication determined as "yes, related", "possibly related" or "Unknown" related to the LV MSP feature will be included as a LV MSP feature-related complication.

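### Section 10.3 stops data collection for every withdrawn subject, so those who leave for explant or by physician decision but still consent lose their later outcomes

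*Combined protocol and SAP*

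**What the plan says.** Section 10.3 gives an open list of possible reasons for withdrawal. Besides withdrawn consent and loss to follow-up, it names "physician discretion" and "CRT-D device or LV lead explant". It then rules: "Additional data can no longer be collected after the point at which a subject has been withdrawn from the study or withdraws his/her consent". The rule covers anyone "withdrawn from the study or withdraws his/her consent, regardless of the reason". What was recorded earlier is kept: "Data collected up to the point of subject withdrawal may be used". For withdrawals caused by device problems there is one further step: "If such withdrawal is due to problems related to the device safety or performance, the investigator shall ask for the subject's permission to follow". That follow-up takes place outside the study, and the plan gives it no route into either endpoint.

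Therapy stopped by reprogramming is handled differently. Under 11.5.14 LV MSP may be turned off for worsening symptoms, and "The subject may continue to receive conventional CRT". Section 11.8 follows non-responders to the 12 Month Visit whether or not LV MSP was on, and 12.1.2.3 analyses LV MSP Group subjects with less than 6 months of therapy.

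In the analysis, 12.1.2.3 treats incomplete paired CCS data as missing and plans a tipping point analysis. Section 12.1.1.3 censors subjects who leave before 180 days without an endpoint event and adds: "Because non-informative censoring cannot be assumed for these subjects, a tipping point analysis will be performed".

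**The concern.** Only withdrawal of consent obliges a trial to stop collecting data. Section 10.3 distinguishes being withdrawn from withdrawing consent, then treats both alike. A subject explanted or removed by the physician after the 6 Month Visit could still supply vital status, HF events, NYHA class and PGA, none of which needs a working LV MSP system.

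What happens next depends on how therapy ended. If LV MSP is switched off, the subject stays and is scored. If therapy ends by explant and the site records a withdrawal, the 12-month score is lost. Exits of this kind may well be related to outcome, so the rule adds to missing data that are probably informative and could have been avoided.

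Two details add to this. Section 12.1.2.3 makes no exception for a subject with an HF event before exit, although 11.6.1.4 already makes that subject Worsened. It also does not say whether subjects with missing data stay in the primary denominator.

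**Working it through.** **Plan's own figures.** Section 12.3 gives 586 enrolled, 10% exit before 6 months, 70% responders, 15% without two viable vectors, 10% below 93% LV pacing and 8% exit between 6 and 12 months.

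- 586 × 0.90 × 0.30 × 0.85 = 134 with LV MSP on.
- 134.5 × 0.90 × 0.92 = 111. By the flowchart counts, 158 − 24 − 10 − 14 = 110. This agrees with the 110 in 12.1.2.2.
- The 8% exit is about 10 subjects. No split by reason is given.
- Exact binomial test, goal 5%, one-sided 5%, n = 110: success needs 10 or more Improved, since P(X ≥ 10 | 110, 0.05) = 4.92%. Power is P(X ≥ 10 | 110, 0.15) = 97.6%, against the stated 95%.

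**Effectiveness bound.** Assume that all 10 exits would have belonged to the LV MSP Group and that all are non-responders. The one-sided 95% exact lower limit for x of n is the 5th percentile of Beta(x, n − x + 1).

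| Improved / n | Lower limit | Goal 5% |
|---|---|---|
| 10 / 110 | 5.02% | pass |
| 10 / 120 | 4.59% | fail |
| 11 / 120 | 5.23% | pass |

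The pass mark rises by one subject. With a 15% rate in the 110 completers, power becomes P(X ≥ 11 | 110, 0.15) = 95.2%.

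Type I error, if the true rate in all 120 is 5% and every exit is a non-responder:

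- Completer rate = 0.05 × 120 / 110 = 5.45%.
- Complete-case rule: P(X ≥ 10 | 110, 0.0545) = 7.8%.
- Exits counted as non-responders: P(X ≥ 11 | 110, 0.0545) = 3.8%.

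If only some of the 10 exits are recoverable, the effect is smaller. With an assumed 2 or 5 such exits, the same formula gives completer rates of 0.05 × 112 / 110 = 5.09% and 0.05 × 115 / 110 = 5.23%, and complete-case type I errors of 5.4% and 6.3%.

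**Safety.** Censoring in 12.1.1.3 applies only without a prior endpoint event. Table 20.2-1 counts an event requiring invasive intervention as a complication and gives generator replacement and loss or abandonment of therapy as examples. Problems corrected by reprogramming are clinical observations. An explant for a problem judged related or possibly related to LV MSP, and recorded before exit, is therefore an event. What can be lost is a related problem that becomes a complication only after exit but within 180 days of LV MSP being turned on.

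With 134 subjects and an exact test standing in for Kaplan-Meier, 7 events pass (lower limit 90.4%) and 8 fail (89.5%). At the plan's 98% complication-free rate about 134 × 0.02 = 2.7 events are expected. With a 2% event rate in the other 124 and j hidden events among the 10 exits, the chance that the full count stays within 7 is P(X ≤ 7 − j | 124, 0.02).

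| j | Chance of passing with full data |
|---|---|
| 0 | 99.6% |
| 2 | 96.1% |
| 4 | 76.3% |
| 5 | 54.8% |

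The larger values of j need several exits to have late, related complications. Nothing in the documents suggests that.

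**The case against.** A reader might infer that every therapy-linked exit is censored for safety, or that the clearest treatment failures drop out of both primary analyses. The documents support neither reading.

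- A related complication recorded before withdrawal counts as an event, and 10.3 requires the case report forms up to that point and keeps the data.
- Death is a separate exit category in 10.2 and is classed as Worsened in 11.6.1.4. Switching LV MSP off for worsening symptoms is not a withdrawal.
- The list in 10.3 is permissive and the section discourages withdrawal. Nothing makes an explant a compulsory exit, and the two LV lead items tied to the 6 Month Visit precede LV MSP.

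All of this stands and narrows the point.

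The sponsor can also say that 12.1.1.3 admits informative censoring and that both endpoints have a tipping point analysis. That stands as disclosure, but such an analysis shows how fragile a result is without recovering the outcomes, and neither has a decision rule attached. The size argument has force too: one extra responder is needed at most, and power stays at the planned level.

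Finally, changing 10.3 alone would not be enough. The LV MSP Group requires at least 93% LV MSP pacing (8.2), and the 12 Month Visit is where the LVa and LVb percentages are collected (11.6.7). The fix therefore has to say how an exited subject meets that criterion.

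**Conclusion.** The point holds in limited form. Section 10.3 discards later outcomes of subjects who still consent, and the plan gives no reason for doing so. For effectiveness these subjects become missing. For safety the loss is confined to related complications that first arise after exit and within 180 days.

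The size is uncertain because exits are not split by reason. The effectiveness bound (one more responder needed, type I error 7.8% against the 5% in 12.4.4, power 95.2%) assumes that all 10 exits belong to the LV MSP Group, that all are non-responders, and that the primary test is complete-case. The plan does not state the last of these outright, though 12.1.2.2 sizes the test on subjects with paired data. The realistic effect is smaller. This is a cheap improvement that prevents avoidable missing data. It does not show that the study's conclusions would be wrong.

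**What to change.** 1. **Section 10.3.** Restrict the stop on data collection to subjects who withdraw consent for it. Loss to follow-up remains unavoidable.
2. **Section 10.3.** For non-responders with LV MSP ever on who have an explant or physician-discretion event after the 6 Month Visit, record end of study therapy instead of study withdrawal. With consent, continue adverse event, hospitalization, vital status, NYHA and PGA collection inside the study through the existing 12 Month Visit.
3. **Section 12.1.2.3.** State that these subjects stay in the effectiveness analysis, with the 93% LV MSP pacing criterion assessed on pacing data up to the end of therapy. Section 11.7 already records percent LV pacing before a counter reset.
4. **Section 12.1.2.3.** State that an HF event before exit classifies the subject as Worsened, not missing.

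The cost is protocol and consent-form wording and follow-up of a few subjects at a visit that 8.1 places within regular clinic care. A few more failures or complications may be counted. No clinical management changes.

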10.4. Subject Status and Classification

All patients who meet all study eligibility criteria, and sign and date an informed consent form are considered enrolled in the study.

Enrolled subjects will be classified as follows:

- Active enrolled - subject who completes the Informed Consent process, signs and dates the ICF and meets the eligibility criteria. Active enrolled subjects will be counted towards the enrollment ceiling.
- Consented and ineligible – subject who signs Informed Consent but does not meet the eligibility criteria.

10.5. Enrollment Controls

Approximately 586 subjects will be enrolled in the study. Study sites will be notified when the enrollment ceiling is close to being reached and once enrollment is complete. No single

site shall enroll more than 20% of the study subjects without the prior written approval from BSC.

11. Study Methods

11.1. *Data Collection*

The data collection schedule is shown in **Table 11.1-1**

Table 11.1-1: Data Collection Schedule

Procedure/Assessment	Enrollment Visit (between 1 day and 21 days post-CRT-D implantation)	Follow-up Visits		
		6 Month Office Visit (183 days post- enrollment -30 days/+0 day)	12 Month Office Visit (183 days post- 6 Month Visit -0 day/+30 days)	Additional Visit
Informed consent process, including informed consent signature and date	X	--	--	--
Inclusion and exclusion	X	--	--	--
Demographics	X	--	--	--
Medical history and medication	X	--	--	--
NYHA Class	X	X	X	--
Patient Global Assessment (PGA), Physician Global Assessment (PhGA)	--	X	X	--
Adverse Events Assessment	X	X	X	X
HeartLogic Alert (required if the feature is enabled)	X	X	X	--
Echo measurement, required only if performed by standard of care	X	X	X	--
Device settings and status	X	X	X	X
Lead measurements (RA, RV, and LV*)	X	X	X	O
SmartDelay test and value, ECG/EGM	X	X	X	--
LV VectorGuide test and value	X**	X***	X****	--
RVp-LVs interval test, ECG/EGM	X	X	X	--
SmartVector test and value	--	X (Non-Responder Group with LV MSP on)	X (Non-Responder Group with LV MSP on)	--
SmartOffset test and value	--	X (Non-Responder Group with LV MSP on)	X (Non-Responder Group with LV MSP on)	--
Battery Consumption	X	X	X	--
LV lead location	X*****	--	--	--
Sleep Incline Trend calibration	X*****	--	--	--

Procedure/Assessment	Enrollment Visit (between 1 day and 21 days post-CRT-D implantation)	Follow-up Visits		
		6 Month Office Visit (183 days post-enrollment -30 days/+0 day)	12 Month Office Visit (183 days post-6 Month Visit -0 day/+30 days)	Additional Visit
“Save all” device data	--	X*****	X*****	--

X = Required; -- = Not required/ Not applicable; O = Optional.

* The LV pacing configuration for lead measurements is per investigator discretion

** It is required to start the LV VectorGuide test at Enrollment Visit in order to measure the RV-LV intervals; however, it is not required to complete the LV VectorGuide test.

*** For subjects in the Responder Group, it is required to start the LV VectorGuide test at the 6 Month Visit in order to measure the RV-LV intervals; however, it is not required to complete the LV VectorGuide test. For subjects in the Non-Responder Group, LV VectorGuide test is required.

**** For subjects in the Non-Responder Group who did not receive LV MSP therapy, it is required to start the LV VectorGuide test at the 12 Month Visit in order to measure the RV-LV intervals; however, it is not required to complete the LV VectorGuide test. For subjects who received LV MSP therapy, LV VectorGuide test is required.

***** Required if the LV lead location information is available through imaging or patient’s medical record.

***** Sleep Incline Trend calibration is not required if the Sleep Incline Sensor is initializing or if the trend is already calibrated prior to this visit.

***** “Save All” device data collection is only required for subjects not enrolled on LATITUDE Remote Monitoring System.

